## **7. Statistical analysis**

All of the data were analyzed using IBM SPSS Statistics 21. The data gathered from the control and the groups were compared using t-test for the mean and standard deviation. A chi-square statistic were used to investigate whether distributions of categorical variables differ from one another. The significance level used in this study was 0.05 for all of the statistical test.

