### ***Plaque index***

Mean of plaque index for all surfaces in baseline were not different ( $P > 0.05$ ). Analyzed from each surface of each sextant, right and left upper lingual posterior surfaces had statistically different mean plaque index ( $P < 0.05$ ) with the higher number of dental plaque in intervention group. However, the anterior upper labial surface of control group had approximately 0.4 points higher number of plaque index than the control group ( $P < 0.05$ ). In follow up mean of plaque index for all surfaces were significantly different ( $P < 0.05$ ) between groups. All of the mean plaque index in intervention group analyzed from every sextant had lower score than the control group and almost all of them were statistically significant ( $P < 0.05$ ).

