### ***Gingival Index***

In baseline, there was no differences in mean of plaque index between groups ( $P > 0.05$ ). The intervention group had significant lower mean of gingival index than the control group ( $P < 0.05$ ).

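### Follow-up plaque index is compared between the two schools without the baseline score that was collected (gingival index by inference); add a post hoc ANCOVA with the change-score contrast beside it, printed with the two-school limit

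*Combined protocol and SAP*

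**What the plan says.** Section 7 (Statistical analysis) names a t-test and a chi-square test, both at the 0.05 level: "The data gathered from the control and the groups were compared using t-test for the mean and standard deviation". It does not say whether the t-test is on follow-up scores or on change, and it names no covariate or model.

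Section 8, Plaque index, shows what was done. Baseline means were tested on their own: "Mean of plaque index for all surfaces in baseline were not different" (P > 0.05). Follow-up means were then tested on their own: "In follow up mean of plaque index for all surfaces were significantly different" (P < 0.05).

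By sextant, three upper surfaces differed at baseline (P < 0.05). Of two it says "right and left upper lingual posterior surfaces had statistically different mean plaque index", with more plaque in the intervention group. Of the third it says "the anterior upper labial surface of control group had approximately 0.4 points higher number of plaque index than the control group", which sets control against control. At follow-up, "All of the mean plaque index in intervention group analyzed from every sextant had lower score than the control group", and almost all of these differences were significant.

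Section 8, Gingival Index, says "The intervention group had significant lower mean of gingival index than the control group" without a time point. Its baseline sentence reads "In baseline, there was no differences in mean of plaque index between groups", so it names plaque under the gingival heading, probably by a slip.

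Section 6 says that both indices were recorded at baseline and at one month in order to follow change. It also says that one school went to each arm by coin flip. Section 8 gives 62 children per arm and follow-up missing for 2 control and 4 intervention children, whose baseline values were carried forward. Section 5 (Specific objectives) adds a before-after comparison in children using the Modified Circular method.

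**The concern.** The baseline score of the same index is usually the best single predictor of the follow-up score, and here it was measured by the same examination. Leaving it out of the between-arm contrast has two effects.

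- **Carry-over.** If the arms differ at baseline by a gap g (in SD), the unadjusted follow-up difference contains r × g that has nothing to do with the brushing method. A non-significant baseline test does not show that g is small.
- **Precision.** The child-level interval is wider than it need be.

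The sextant results are the most exposed, because baseline differences are reported there. On the two upper lingual posterior surfaces, carry-over hides part of any benefit. On the upper anterior labial surface, it exaggerates benefit if control was the higher group, which is the likely but unconfirmed reading.

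The before-after objective has a related weakness. Both arms received motivation, a toothbrush and toothpaste, and instruction on brushing frequency and duration. A change in the intervention arm alone therefore cannot be credited to the method.

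**Working it through.** **Inputs.** From the documents: 62 children per arm, 60 control and 58 intervention with observed follow-up, alpha 0.05 (taken as two-sided), one school per arm, and a baseline gap of about 0.4 points on one surface. Not given, so assumed: r = 0.3, 0.5 or 0.7, equal SDs, and intraclass correlation (ICC) 0.01 to 0.05. The plan states no sample-size or precision figure, so there is none to reproduce.

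**1. Largest gap that still gives P > 0.05.** t(0.975, 122) × √(2/62) = 1.980 × 0.1796 = 0.356 SD. This is also the unadjusted 95% CI half-width at follow-up.

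**2. Child-level precision, no school variation.** ANCOVA half-width = t(0.975, 121) × √(2(1 − r²)/62). Change-score half-width = 1.980 × √(4(1 − r)/62).

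| | r = 0.3 | r = 0.5 | r = 0.7 |
|---|---|---|---|
| t-test on follow-up (SD) | 0.356 | 0.356 | 0.356 |
| ANCOVA (SD) | 0.339 | 0.308 | 0.254 |
| Change score (SD) | 0.421 | 0.356 | 0.275 |
| ANCOVA, 60 v 58 observed (SD) | 0.348 | 0.316 | 0.260 |

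With 60 and 58 children the t-test half-width is 1.981 × √(1/60 + 1/58) = 0.365 SD.

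**3. Overall PI, no method effect, chance gap.** Take baseline and follow-up test statistics as bivariate normal with correlation r. Given baseline P > 0.05, the follow-up t-test rejects in 4.7%, 4.3% or 3.5% of cases, so there is no inflation on average.

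**4. Surfaces with baseline P < 0.05, no method effect, chance gap.** The follow-up t-test rejects in 9.8%, 18.5% or 33.1% of cases. Nearly all of these lie in the direction of the baseline gap; the opposite direction accounts for 0.3% or less. On the two lingual surfaces the baseline gap ran against the intervention arm, yet its follow-up means were lower, so carry-over works against the reported result. The figure can favour that result on at most one surface, the upper anterior labial. There a 0.4-point gap carries 0.4 × r = 0.12, 0.20 or 0.28 points.

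**5. If the gap is a lasting school difference.** Take 0.356 SD at both visits and no method effect. ANCOVA leaves (1 − r) × 0.356 = 0.249, 0.178 or 0.107 SD and rejects in about 30%, 20% or 13% of cases, against 50% for the t-test. The change-score contrast removes the gap and rejects in about 5%.

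**6. School variation omitted by every child-level interval.** Factor by which the SE is too small:

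- t-test: √(1 + 61 × ICC) = √1.61 to √4.05 = 1.27 to 2.01.
- ANCOVA, school variation arising after baseline: √(1 + 62 × ICC / [(1 − ICC)(1 − r²)]) = 1.30 (ICC 0.01, r 0.3) to 2.72 (ICC 0.05, r 0.7).
- ANCOVA, school difference persisting from baseline: the ICC term is multiplied by (1 − r)², giving 1.05 (ICC 0.01, r 0.7) to 1.66 (ICC 0.05, r 0.3).

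The t-test line uses the usual design effect on total variance. On the within-school basis of the ANCOVA lines it would be 1.28 to 2.06.

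A null simulation with r = 0.5 and a residual school ICC of 0.02 gave type I error of 16% for the t-test and 20% for ANCOVA.

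**The case against.** The strongest case against has four parts.

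- **The t-test is valid without a baseline covariate.** This stands at child level. A reader might infer that the reported overall PI difference is a false positive, or that adjustment would overturn it. The documents do not support that: overall baseline PI is reported as not different, step 3 shows no average inflation, and no means, SDs or correlations are given from which a changed conclusion could be shown.
- **One school per arm is the larger problem, and ANCOVA does not touch it.** This stands. A reader might take the narrower interval as stronger evidence for the method. It is not: the child-level interval is already too short for a method effect, and ANCOVA can shorten it further relative to the true uncertainty. Precision is a real gain only for the child-level contrast between these two schools.
- **ANCOVA is not the only choice.** This stands in part. The study calls itself quasi-experimental and compares two intact schools, so a gap need not be chance. Change scores remove a lasting gap but cost precision at low r. Neither method dominates, so both should be shown.
- **Carried-forward values equal the covariate.** True for six children, which is why those with observed follow-up should be analysed first.

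The baseline data are not wholly unused: they are tested separately and fill the six missing values. They are not used to adjust the contrast.

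**Conclusion.** The concern holds in a limited form. PI was compared between the schools on follow-up means, and the baseline score of the same index was left out. The same is likely for GI but cannot be confirmed. The contrast therefore carries r times any baseline gap.

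The consequence is clearest on three upper surfaces: any benefit is understated on two, and overstated on the third if control was higher there. At child level, and with no school variation, the unadjusted half-width is 0.356 SD where ANCOVA would give 0.254 to 0.339 SD for r between 0.7 and 0.3.

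These sizes rest on assumed correlations, equal SDs and independent children; the school-variation factors rest on an assumed ICC. This is a cheap improvement to a reported analysis. It neither refutes the result nor remedies the two-school design.

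**What to change.** Keep the t-test as reported and add, labelled as post hoc and specified after the results were known:

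1. ANCOVA of follow-up PI, and separately of follow-up GI, on arm plus the baseline score of the same index, giving the adjusted difference and 95% CI. Run it first in the 118 children with observed follow-up (60 control, 58 intervention), then in all 124 with carried-forward values as a sensitivity analysis.
2. Beside it, as a further sensitivity analysis, the between-arm difference in change with 95% CI.
3. Sextant results analysed in the same way and called exploratory.
4. With every result, this sentence: *With one school per arm this comparison cannot separate school from method, and its interval omits between-school variation.* Quote the school-variation factors separately for the t-test and for ANCOVA, with the ICC and r stated as assumptions.
5. The control arm's change shown next to the intervention arm's before-after comparison, with the latter treated as descriptive.

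In the text, state in section 7 which score the t-test used, correct the control-against-control sentence, give the time point for the GI result, and correct the index named in its baseline sentence.

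The cost is a few regressions in the same software on data already held. The downside is that the analysis is post hoc and its narrower interval can look more certain than two schools allow, so the limiting sentence must be printed with it.

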### Specific objectives

- a. To compare level of plaque before and after using the Modified Circular tooth brushing method.
- b. To compare level of gingivitis before and after using the Modified Circular tooth brushing method.

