#### Dependent Variables and Data Collection

The dependent variables in this study were Plaque Index (PI) and Gingival Index (GI). The hypotheses of this study were the plaque level and gingivitis level in subjects using the Modified Circular method is different from that in subjects using natural tooth brushing method and the level of plaque after using the Modified Circular method is different from that before using the method.

*Plaque Index Examination.* Participants' plaque level was measured using Turesky Modification of Quigley Hein (83). Data were collected during baseline and follow-up to track the changing of the plaque level before and after intervention. The tools used in this examination were micro-brush, mouth mirror and probe under the natural light. The procedure was painting all of the exposed tooth surfaces with disclosing solution and the participants were asked to rinse one time. Facial and lingual surfaces of the teeth were examined except third molars. A score between 0 and 5 was given based on the criteria. The plaque scores were recorded on the plaque index examination sheet containing the diagram of the teeth with the separated boxes of facial and lingual/palatal areas. The index was determined by calculating the total score divided by the numbers of the surfaces examined.

Table 1 Scoring criteria of Turesky Modification of Quigley-Hein Index (83)

Score	Criteria
0	No plaque.
1	Separate flecks of plaque at the cervical margin of the tooth.
2	A thin continuous band of plaque (up to one mm) at the cervical margin of the tooth.
3	A band of plaque wider than one mm but covering less than one-third of the crown of the tooth.
4	Plaque covering at least one third but less than two thirds of the crown of the tooth.
5	Plaque covering two-thirds or more of the crown of the tooth.

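### The before/after objectives and the second hypothesis have no matching test in section 7 and no result in section 8, and the size of the between-group effect is not reported

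*Combined protocol and SAP*

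**What the plan says.** The general objectives in section 5 compare plaque and gingivitis between the two brushing groups. The specific objectives ask a different question, within the Modified Circular group: "To compare level of plaque before and after using the Modified Circular tooth brushing method" and "To compare level of gingivitis before and after using the Modified Circular tooth brushing method". Under Dependent Variables and Data Collection in section 6, the second hypothesis is that "the level of plaque after using the Modified Circular method is different from that before using the method"; it covers plaque only. The same section gives the purpose of measuring twice: "Data were collected during baseline and follow-up to track the changing of the plaque level before and after intervention". The Gingival Index paragraph says the equivalent for gingival condition.

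Section 7 has one sentence on means: "The data gathered from the control and the groups were compared using t-test for the mean and standard deviation". The other named test is for categorical data: "A chi-square statistic were used to investigate whether distributions of categorical variables differ from one another". The level is set once: "The significance level used in this study was 0.05 for all of the statistical test".

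Section 8 then reports, on plaque, that "In follow up mean of plaque index for all surfaces were significantly different" between groups. It adds that every sextant mean was lower in the intervention group, almost all of them significantly. On gingivitis it says the intervention group had the significantly lower mean.

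**The concern.** A before/after question is about the same child at two visits. It is answered from within-child differences. A comparison of one school's children with another's does not answer it. If the plan names only the group comparison and the results contain only group comparisons, the specific objectives and the second hypothesis are stated and then left without an answer.

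A second gap concerns the general objectives. They ask about the level of plaque and gingivitis. A direction and a significance statement do not tell the reader how far apart the groups were on the 0 to 5 plaque scale or the 0 to 3 gingival scale, so a small difference cannot be told from a large one.

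**Working it through.** There is no design figure to reproduce: the document gives no sample-size calculation, assumed effect or SD. The check is mainly a matching of questions to tests and results.

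**1. Questions against tests and results**

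| Question | Test in section 7 | Result in section 8 |
|---|---|---|
| Plaque, between groups (general objective a) | t-test worded as a group comparison | Lower in intervention group, P < 0.05; no mean, SD, difference or CI |
| Gingivitis, between groups (general objective b) | Same | Lower in intervention group, P < 0.05; no mean, SD, difference or CI; time point not named |
| Plaque, before/after (specific objective a, second hypothesis) | None named | None |
| Gingivitis, before/after (specific objective b) | None named | None |

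The chi-square test is for categorical variables and does not address change in a mean index. Specific objective b also has no corresponding hypothesis.

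**2. Whether a magnitude appears anywhere**

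The only index difference with a number is about 0.4 points on the anterior upper labial surface. It stands before the sentence on follow-up, so it is a baseline figure. As printed, it compares the control group with itself. It says nothing about the effect at follow-up.

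**3. What P < 0.05 alone implies**

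Inputs: 62 per group analysed (section 8) and level 0.05 (section 7). Two assumptions are mine: the test is two-sided, and children are independent.

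- Smallest significant standardised difference = t(0.975, 122) × √(2/62) = 1.980 × 0.1796 = 0.356 SD.
- On observed follow-up only (62 − 2 = 60 control, 62 − 4 = 58 intervention): t(0.975, 116) × √(1/60 + 1/58) = 1.981 × 0.1841 = 0.365 SD.

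This is a lower bound with no upper limit. It cannot be put into index points, because no SD is given. It is also optimistic, because each arm is a single school.

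**4. Effect of the filled-in values on a before/after analysis**

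Section 8 replaces missing follow-up with the baseline value. For 4 of the 62 intervention children (4/62 = 6.5%) the change is therefore exactly zero. The mean change over all 62 equals 58/62 = 0.935 times the mean change in the 58 observed children. The shift is small, but both figures should be shown.

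**The case against.** The strongest reply has four parts.

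- **Section 7 says only t-test.** It specifies neither independent nor paired, in a sentence that is plainly garbled. A paired test may have been intended, since the data were collected at both visits to follow change. This stands to a degree: the fair conclusion is that the before/after test is unspecified. A reader might go further and infer that a two-sample test was run on paired scores, treating each child as two independent ones. Nothing in the document says so. No before/after analysis is reported at all, so there is no such error to size.

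- **The results are more than bare P values.** This stands. Section 8 gives the direction for both indices and for every sextant. A reader might say that only a threshold was reported, but that would be wrong. What is missing is the size.

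- **Nothing shows that the effects are small.** This also stands. A reader might take the 0.356 SD bound as a sign of a modest effect, or turn it into index points with a guessed SD. It is only the minimum compatible with P < 0.05, and the document supplies no SD.

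- **Section 8 is a short narrative, and some pages of the file were not available for this check.** Section 8 refers to no table or figure. If a results table exists, section 8 should cite it. The missing before/after test in section 7 would remain.

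**Conclusion.** The point holds as an omission in both plan and report. Two of the four objectives and the second hypothesis have no named test and no result. The two between-group objectives have a direction and P < 0.05, but the effect size is unknown beyond a lower bound of about 0.36 SD. That bound assumes a two-sided test and independent children.

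The document does not support saying that a wrong test was applied, that the reported direction is mistaken, or that the effect is small. The conclusion rests on the text of sections 5 to 8 as available. It should be corrected, because the study cannot otherwise answer questions it set itself.

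**What to change.** **Section 7.**

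- For the Modified Circular group, add a paired t-test on each child's own change in Plaque Index and Gingival Index, reporting mean change and 95% CI. Show it for all 62 children and for the 58 with observed follow-up, and state that 4 follow-up values are copied from baseline.
- State the between-group comparison as the mean difference in each index at follow-up with 95% CI. Adjustment for the child's baseline value is preferable, since section 8 reports significant baseline differences on some surfaces.
- State that a group effect will not be inferred by comparing within-group P values.

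**Section 8.** Print mean, SD, change and 95% CI for both indices at both visits, and name the visit for the gingival result. Beside the intervals, note that a coin flip allocated one school to each arm (Experimental Design). Child-level intervals are therefore too narrow and cannot separate the method from the school.

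**Cost.** A few sentences in section 7 and one table. No new data are needed: the data collection procedure says follow-up repeated the baseline measurements. The before/after analysis would be specified after the results are known, and should be labelled so.

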Tooth brushing will be effective in removing the dental plaque if it is done with the sufficient duration at least 2 minutes (16). Frequency of tooth brushing is recommended to be done twice a day (17). Tooth brushing type that is used to brush is recommended using manual tooth brush with small-headed toothbrush, soft round-ended filaments and comfortable handle (18). There are several factors from individual that may cause the differences in effectiveness of tooth brushing in plaque removal such as age, education, and socioeconomic status (13, 19, 20).

People, without any training, naturally brush their teeth using horizontal scrub, a rotary motion, or simple up and down (21). Many people using natural motion of tooth brushing can produce good oral environment that inhospitable to biofilm without any damaging effect in their tissue (21, 22). Asadoorian (15) estimated that over 90% of people employ their natural tooth brushing method that is personally built. This method will remove plaque from smooth surfaces of the teeth, but this method have limitation that is considered detrimental because it can cause gingival recession and tooth abrasion (23). People will pay poor attention to the lingual areas of their teeth while practicing this method probably because these areas do not affect the aesthetics and tend to difficult to be accessed (24).

A systematic review by Muller-Bolla and Courson (25) showed that in early mixed dentition stage, the most effective tooth brushing technique is horizontal technique. McClure (26) comparing tooth brushing efficacy between horizontal Scrub and modified Bass method in children aged 10-12 years old reported there were no significant differences in plaque removal ( $P > 0.01$ ) between two methods. Robinson (27) evaluated plaque removal of Scrub and Bass methods in children aged 12-13 years old and found that there were no differences between two methods. Smutkeeree et al. (28) found that there were no significant differences in gingival condition (Gingivitis Index) between Horizontal Scrub and Modified Bass groups ( $P > 0.05$ ) in children aged

10-12 years old. However, the studies about tooth brushing method recommended for children in late mixed dentition aged are still limited.

[figure not shown]

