*Gingival Index Examination.* The examination of gingival condition was using the Gingival Index (88). Data were collected during baseline and follow-up to track the changing of the gingival condition before and after intervention. The tools used in this examination were mouth mirror under the natural light. The procedure was examining all of the gingiva on the buccal, lingual/palatal, mesial, and distal areas of the teeth. A score between 0 and 3 was given based on the criteria. The Gingival Index were recorded on the gingival index examination sheet containing the diagram of the teeth with the separated boxes of buccal, lingual/palatal, mesial, and distal areas. The index was determined by calculating the total score divided by the numbers of the areas examined.

Table 2 Scoring criteria of Gingival Index (88)

Score	Criteria
0	Normal gingiva.
1	Mild inflammation - slight change in color, slight edema. No bleeding on probing.
2	Moderate inflammation - redness, edema and glazing. Bleeding on probing.
3	Severe inflammation - marked redness and edema. Ulceration. Tendency to spontaneous bleeding.

*Questionnaire.* Personal information; oral health knowledge, attitudes, practices; and eating habits of the participants were recorded using questionnaire. The questionnaire were questioned by interview. Data were collected during baseline and follow-up to check the changing of tooth brushing practice and eating habit that may influence the plaque and gingival index. The back-translation technique had been used to ensure the quality between the English and Indonesian language versions. The interviewer marked

X on the box of questionnaire choice of answers in accordance with the answers of participants.

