### Experimental Design

The research was using a quasi-experimental study design. Data were gathered from two groups of subjects. This research was a single-blind study which the examiner will be blinded to the allocation of subjects.

This study began with selecting two elementary schools in the same district in Yogyakarta, Indonesia, that have similarity in socio-economic status and the number of the students based on the data and recommendation of Technical Education Service Unit of Yogyakarta. The schools met the criteria that was not under any plans of getting other interventions of dental health program during one month intervention period of this study. All of the fifth graders of the selected schools participated the study. With the coin flipping method, a school was allocated to be intervention group and the other was being the control group. The participants had been informed about the purpose of the study, the procedure, and the right to continue or withdrawn without any penalties. The participants had given consent to follow the study.

The study began with the baseline data collection. Then it continued with the training for the participants about improving the oral hygiene. In this stage, the intervention group was demonstrated and instructed to brush their teeth using Modified Circular method, while the control group was not given any instruction to brush their teeth using a specific tooth brushing method and asked to brush their teeth using the way they brushed every day. The period of intervention was started after training and lasted for one month. In intervention period, intervention group was observed once a week to ensure that they brushed their teeth correctly using Modified Circular method. Finally the evaluation was implemented after 1 month of intervention.

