## **8. Results**

At the beginning of the study, participants who participated in this study amounted to 62 children for control group and 62 children in experimental group. There was no number of excluded participants. The schools was not under any plans of getting other interventions of dental health program during one month intervention period of this study. After random assignment of the groups, all of the participants received the intervention. Lost to follow-up were found with the number of 2 in control group and 4 in intervention group. The participants did not come in the day of follow-up data collection with the reason of sick and family occasion. Using the intention-to-treat method, the number of data analyzed were following the original number allocated, that were 62 for each group. The missing value in follow-up were replaced using the last value obtained, in this case the baseline value was used.

The age of the participants and the percentage of male and female participants between control and intervention group were not significantly different ( $P < 0.05$ ). The

tooth brushing habit of the participants seen from the frequency and the duration of brushing were not significantly different ( $P < 0.05$ ). Snacking and eating frequency that reflected the eating habit of the participants were also not different ( $P < 0.05$ ).

In this study, all of the participants (100%) in the control group can follow the protocol to brush their teeth using natural method. In intervention group, 79% of the participants followed the protocol to brush their teeth using Modified Brush tooth brushing method systematically.

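### The two-school comparison uses an unadjusted t-test although baseline factors that the document names as influences on plaque were collected; the resulting bias is possible, not shown, and a covariate-adjusted model should be added

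*Combined protocol and SAP*

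**What the plan says.** Section 7 (Statistical analysis) gives one method for the indices: "The data gathered from the control and the groups were compared using t-test for the mean and standard deviation". For categorical variables it adds: "A chi-square statistic were used to investigate whether distributions of categorical variables differ from one another". It names no regression, analysis of covariance, stratification or school term.

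The Experimental Design part of Section 6 describes the allocation: "The research was using a quasi-experimental study design", and "With the coin flipping method, a school was allocated to be intervention group and the other was being the control group". The arm is therefore a school, and there is one school on each side.

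The document names influences on the outcome in two places. Section 3 refers to "several factors from individual that may cause the differences in effectiveness of tooth brushing in plaque removal such as age, education, and socioeconomic status". The questionnaire paragraph under Dependent Variables and Data Collection refers to "tooth brushing practice and eating habit that may influence the plaque and gingival index", with data taken at baseline and follow-up so that changes in them could be checked.

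Section 8 uses these data only to compare the groups. Age and sex, and brushing frequency and duration, are reported as showing no significant difference. For diet it says: "Snacking and eating frequency that reflected the eating habit of the participants were also not different". All three statements carry P < 0.05 in brackets.

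**The concern.** A single coin flip between two schools decides which school gets the training. It does not spread the children's characteristics evenly over the arms, as randomising individual children would tend to do. If one school's pupils are somewhat older, brush more often or snack less, that difference passes into the unadjusted follow-up contrast and is read as an effect of the brushing method.

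The document identified such factors and measured them, but used them only as a balance check. A non-significant balance test in a sample this size is weak evidence of balance, and the contradictory P values mean that even this evidence cannot be taken as printed.

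**Working it through.** The documents give no sample-size calculation, SD, correlation or covariate mean. There is no stated figure to reproduce, and no adjusted estimate can be computed. What can be checked is how much imbalance the balance tests could miss and what it would do.

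**Inputs.** 62 children per group (Section 8). Significance level: "The significance level used in this study was 0.05 for all of the statistical test" (Section 7). Sidedness is not stated; I take it as two-sided. Correlations between a factor and the index are my assumptions.

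**1. Largest gap that still passes a balance test.**
- Standard error of a standardised difference: sqrt(2/62) = 0.180.
- Continuous factor: t(0.975, 122) × sqrt(2/62) = 1.980 × 0.1796 = 0.356 SD.
- Yes/no factor near 50%: 1.96 × sqrt(2 × 0.25/62) = 0.176, about 17.6 percentage points.

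**2. Power of the balance test.** With 62 per group it is about 20% for a true gap of 0.2 SD and about 50% for 0.35 SD. It reaches 80% only at (1.96 + 0.84) × 0.180 = 0.50 SD.

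**3. Shift in the unadjusted contrast.** Bias in SD of the index = gap × r, where r is the within-group correlation of the factor with the index.
- r = 0.2: 0.2 × 0.356 = 0.07 SD.
- r = 0.4: 0.4 × 0.356 = 0.14 SD.

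The smallest index difference that reaches P < 0.05 is also 0.356 SD, so these shifts are 20% and 40% of it.

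**4. Wider range.** For gaps of 0.1 to 0.35 SD and r of 0.1 to 0.5, the bias runs from 0.1 × 0.1 = 0.01 SD to 0.35 × 0.5 = 0.175 SD. With no true method effect, and ignoring clustering, the rejection rate then lies between 5.0% and 16.4%. At a gap of 0.35 SD and r = 0.3, the bias is 0.105 SD, or 0.105/0.180 = 0.58 standard errors, and the rejection rate is 9.0%.

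**5. Effect of adjusting for the baseline index.** Suppose a factor acts on the baseline and follow-up index with the same r, and the two index values correlate ρ within groups with equal variance. The remaining bias is then gap × r × (1 − ρ), which is smaller than in step 3 for any positive ρ. The documents give no ρ, so I put no figure on it.

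**6. What adjustment cannot reach.** Arm and school are the same variable, so no covariate model separates them. For scale, if the intraclass correlation were 0.01 to 0.05, the design effect 1 + 61 × ICC would be 1.6 to 4.1, and a nominal 5% child-level test would reject about 12% to 33% of the time under no effect.

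**7. The printed P values.** Steps 1 and 3 use the wording in Section 8, that is, P > 0.05. If the printed P < 0.05 is correct instead, the 0.356 SD ceiling does not apply and the gaps would be larger. The text and the P values must be reconciled first.

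**The case against.** The design has real controls. All participants are fifth graders aged 10 to 12, which narrows age and schooling. The schools lie in one cluster and were chosen as similar in socio-economic terms, number of students and type (Participants and setting). Both arms were told to brush twice a day for two minutes and received a brush and toothpaste (Data collection procedure), so a baseline gap in frequency or duration need not carry through to follow-up. Overall baseline plaque did not differ significantly (Section 8). The questionnaire's stated purpose was to track change between visits, and sex is not named as an influence. All of this stands. A reader who infers that nothing limits imbalance between the arms goes too far.

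A reader might also stack several factors. Three uncorrelated ones, each at the limit, all in one direction, each with r = 0.3, would give 3 × 0.3 × 0.356 = 0.32 SD, about 90% of the just-significant difference. The documents support none of those conditions, so this is a worst case and not an estimate. The just-significant difference is also not the observed effect, whose size is not reported.

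These controls do not make adjustment unnecessary. Similarity of schools is not matching of children, diet was not standardised, and the test of overall baseline plaque has the same limited power as the other balance tests.

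**Conclusion.** The concern holds in a limited form. Section 7 leaves out baseline factors that the document itself names as possible influences, in a design where chance does not balance them between children. The balance statements cannot settle the matter: gaps up to about 0.36 SD would go unflagged, and the printed P values contradict the text.

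Under the assumed correlations of 0.2 to 0.4, one factor at that limit shifts the plaque contrast by 0.07 to 0.14 SD, and by less after adjustment for the baseline index. This bias is possible but not demonstrated.

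A reader might infer that the reported group differences are due to school composition. The documents do not support that, because they give no covariate means, SDs or correlations and no effect size. Nor would an adjusted model settle the method question: one school per arm leaves school and method confounded.

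**What to change.** Add to Section 7 a linear model of follow-up plaque index, and separately of gingival index, on arm, the baseline value of the same index, and a fixed set of baseline covariates: age, sex, brushing frequency, brushing duration, snacking frequency and eating frequency. Keep the set whatever the balance P values show. Use baseline habits only, since follow-up habits are measured after training and may lie on the causal path.

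Report the adjusted mean difference with its 95% CI beside the unadjusted one, and label it post hoc. In Section 8, reconcile each balance statement with its P value, then replace the balance P values with group summaries and standardised differences.

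State that school and method remain confounded, and that the child-level CI does not reflect variation between schools.

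The cost is re-analysis of data already collected. With one term per covariate, seven degrees of freedom are used and 122 − 7 = 115 remain for error; covariates coded in several categories use a few more. The drawback is that the model is chosen after the results are known, so it serves as a sensitivity analysis and not as confirmation.
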